2. Determine if active tDCS augments cortical excitability after gait training. Cortical excitability will be defined by a cortical recruitment curve, a primary outcome measure, derived from plots of motor evoked potentials (MEPs) recorded from the ipsilesional TA muscle. MEPs are elicited by single pulse transcranial magnetic stimulation (TMS) delivered at increasing intensity over motor cortex. Changes in the slope of the recruitment curve signal change in cortical excitability. Difference scores from baseline will be compared between active and sham groups to determine if tDCS augments cortical excitability after FESAGT. A repeat fMRI will be performed to assess change in cortical excitability after gait training.
3. Determine if active tDCS augments physical function and social wellbeing. The Stroke Impact Scale-16 (SIS-16), a primary outcome measure, will be used to assess ADL/IADL, mobility, and social and occupational engagement at baseline and post treatment assessments. Difference scores from baseline will be compared between active and sham groups to determine if tDCS augments physical function and social well-being.

Exploratory Aim

Identify patient characteristics that predict response to treatment. Patients will be classified empirically based on their response to treatments. Regression analyses will examine whether and how initial impairment, functional level, and cortical excitability predict a treatment response.

Study Interventions

tDCS and gait training will be conducted at UCA three times a week for 4 consecutive weeks

Version 10 Revised 11/21/2014

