- Necessitates medical or surgical intervention to preclude a permanent disability or incapacity
- Results in a congenital anomaly or birth defect

Non-serious adverse events are all events that do not meet the criteria for a “serious” adverse event.

Severity:

Each adverse event will be assessed for its severity, or the intensity of an event experienced by the subject, using the following.

- Mild: Discomfort noticed, but no disruption to daily activity.
- Moderate: Discomfort sufficient to reduce or affect normal daily activity.
- Severe: Inability to work or perform normal daily activity.

Anticipated Adverse Events and Pre-existing conditions:

Pre-existing conditions will not be reported as an adverse event unless there has been a substantial increase in the severity or frequency of the problem which has not been attributed to natural history.

Data Handling and Recordkeeping

Each subject's name, birth date, address and phone number will be obtained for purposes of follow-up. We will ask for each subject's drug use history, medical history, and current drug use. Experimental data and questionnaire data will be collected. This information will be coded into the Microsoft Excel. Each subject's personal information will be de-identified in the database by using codes comprising the subject number and date and time the subject was tested. The PIs and study personnel at UAMS and UCA will have access to subject identities in order to arrange follow-up and to call them as part of the research project, such as follow-up contact. If subjects prefer e-mail correspondence research personnel will send e-mails for scheduling, follow-up, and research-related communication.

Data Analysis

Aims 1-3. Difference scores from baseline will be calculated for each outcome measure. A mixed model ANOVA with group (active tDCS groups versus sham tDCS) as the between subjects factor and time of assessment (pre, weeks 1-4, & one week and one month post) as the within subjects factor will be used to test all aims. A significant group effect, with active tDCS > sham tDCS, for any of the outcome measures would indicate that anodal tDCS augments gait training. A significant main effect of time would be evaluated using planned contrasts where we expect post treatment assessments to be improved relative to baseline. Interim analyses will be completed at critical stages during the protocol.

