Exploratory Aim. We will classify patients as “likely responsive” and “likely unresponsive” to tDCS based on the magnitude of difference scores and compare them to determined patient characteristics that predict a treatment response. Predictors for 88 subjects include 1) NIH Stroke Scale score, 2) initial levels of impairment, 3) initial MT of the contralateral TA muscle (and recruitment curve parameters from the ipsilateral TA muscle), 4) initial SIS-16 total and subscale scores, 5) stroke laterality, and 6) modified Rankin Scale scores. A series of regression analyses will be conducted to reduce the overall number of predictors and to build an initial model, which assess the predictive value or weight of remaining variables, and to cross-validate predictors. To determine which stroke related variables are associated with a response to treatment, brain lesions will be mapped onto templates and analyzed using lesion subtraction techniques with the public domain MRIcro and MRIcron software programs (see Core B). Lesion subtraction will identify the lesion sites that are common to treatment responders and not common to nonresponders.

Ethical Considerations

This study will be conducted in accordance with all applicable government regulations and University of Arkansas for Medical Sciences research policies and procedures. This protocol and any amendments will be submitted and approved by the UAMS Institutional Review Board (IRB) to conduct the study.

The PI or designated staff will discuss the informed consent form with the subject volunteer. The consent process will take place in a quiet and private room. Subjects may take as much time as needed to make a decision about their trial participation and may take the document home if desired. The person obtaining consent will thoroughly explain each element of the document and outline the risks and benefits, alternate treatment(s), and follow-up requirements of the study. Participation privacy will be maintained and questions regarding participation will be answered. No coercion or undue influence will be used in the consent process. No research related procedures will be performed prior to obtaining informed consent. All signatures and dates will be obtained. A copy of the signed consent will be given to the participant. The informed consent process will be documented in each subject’s research record.

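### Exploratory Aim: if response is classed from change in SIS-16 or the recruitment curve, that measure's own listed baseline will tend to look like a predictor when nothing predicts response

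*Combined protocol and SAP*

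**What the plan says.** Four places in the combined protocol and SAP bear on this point.

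- **Data Analysis, Aims 1-3:** "Difference scores from baseline will be calculated for each outcome measure".
- **Specific Aims 2 and 3:** two of these outcomes are named as primary: "Cortical excitability will be defined by a cortical recruitment curve, a primary outcome measure" and "The Stroke Impact Scale-16 (SIS-16), a primary outcome measure". Gait speed (Aim 1) is the third.
- **Exploratory Aim under Specific Aims:** "Patients will be classified empirically based on their response to treatments", and then "Regression analyses will examine whether and how initial impairment, functional level, and cortical excitability predict a treatment response".
- **Data Analysis, Exploratory Aim:** patients are labelled likely responsive or likely unresponsive "based on the magnitude of difference scores and compare them to determined patient characteristics that predict a treatment response". The predictors, listed for all 88 subjects, include "4) initial SIS-16 total and subscale scores" and, beside the initial motor threshold, "and recruitment curve parameters from the ipsilateral TA muscle". The others are NIH Stroke Scale, an undefined entry for initial impairment, stroke laterality and modified Rankin score.

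The aim does not say which outcome's change defines response, or at what cut-off. It specifies no baseline adjustment and no predictor-by-arm term. Cross-validation is the only safeguard named.

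**The concern.** A difference score is follow-up minus baseline. A patient whose baseline was low partly by chance will tend to show a large gain, and one whose baseline was high by chance will tend to show a small one. If the same baseline is then offered as a predictor of being a responder, a negative association appears without any real difference in responsiveness (mathematical coupling and regression to the mean).

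For SIS-16 and the recruitment curve, the plan puts the measure on both sides: its change can define response, and its baseline is a listed predictor. Cross-validation does not help, because the coupling recurs in every fold and the false predictor appears to replicate. Restricting the analysis to the active arm does not help either, so this is separate from the lack of a sham comparison in the aim.

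At stake is the aim's own question, namely which patient characteristics go with response. A finding that worse initial function or lower excitability predicts response to tDCS could arise even if tDCS did nothing.

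**Working it through.** The Exploratory Aim states no figure, so there is none to reproduce. The check asks how often a measure's own baseline looks predictive when there is no treatment effect and no true predictor.

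**Inputs**

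- n = 88 for the predictor analysis (Data Analysis, Exploratory Aim) and 44 per arm (Study Population).
- Correlation r between baseline and follow-up. Power analysis gives 0.60 for gait speed and calls it conservative. No value is given for SIS-16 or the recruitment curve, so r from 0.60 to 0.95 is an assumption.
- Further assumptions: response means signed improvement; baseline and follow-up SDs are equal; responders are those above the median change; baseline is compared between classes by a two-sided t-test at 5%. The plan fixes none of these.
- The ipsilateral tibialis anterior in the predictor list is read as the ipsilesional one used for the Aim 2 outcome.

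**Step 1: correlation of baseline with change.** With equal SDs, corr(baseline, change) = -sqrt((1 - r)/2).

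- r = 0.60: -sqrt(0.40/2) = -0.45
- r = 0.90: -sqrt(0.10/2) = -0.22
- r = 0.95: -sqrt(0.05/2) = -0.16

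**Step 2: false-positive rate, response defined on the same measure.** Simulated null trials give approximately:

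| r | n = 88 | n = 44 (active arm only) |
|---|---|---|
| 0.60 | 94% | 69% |
| 0.75 | 77% | 47% |
| 0.90 | 38% | 21% |
| 0.95 | 21% | 14% |

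Hand check at r = 0.60, n = 88: a median split multiplies the correlation by sqrt(2/π) = 0.798, giving 0.798 × 0.447 = 0.357. Fisher's z is 0.373, and 0.373 × sqrt(85) = 3.44. The chance of exceeding 1.96 is about 93%, in line with the simulation. In the same setting responders start about 0.71 SD lower. About 65% of the low-baseline half are labelled responders, against 35% of the high-baseline half.

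**Step 3: other definitions of response, n = 88**

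- Equally weighted sum of three changes: about 48%, 34% and 16% at r = 0.60, 0.75 and 0.90. If the three changes are independent and equally variable, the correlation falls by sqrt(3), from 0.447 to 0.258 at r = 0.60.
- Gait-speed change alone, with baseline SIS-16 as predictor: about 5%. SIS-16 and gait are correlated at baseline here, but their measurement errors are independent.
- Absolute rather than signed change: about 5%.

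**Step 4: unequal SDs.** With k = follow-up SD / baseline SD, the correlation is (rk - 1)/sqrt(1 + k² - 2rk). At r = 0.60 it is -0.63 for k = 0.8, -0.28 for k = 1.2 and -0.14 for k = 1.4. It vanishes at k = 1/r = 1.67.

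**Step 5: the alternative.** In the same null data at n = 88, follow-up was regressed on baseline, arm and baseline × arm. The interaction was falsely significant in 5.6%, 5.1% and 5.3% of trials at r = 0.60, 0.80 and 0.90.

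**The case against.** The strongest objection is that the problem needs a pairing the plan never states. Coupling arises only when a measure's baseline is set against its own change. Gait speed drives the sample size and is a natural response measure, yet baseline gait speed is not a named predictor. With response on gait speed alone, baseline SIS-16 shows about the nominal error rate. This stands, and it makes the point conditional. It does not dispose of it: the aim does not restrict response to gait, and difference scores are planned for every outcome.

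A reader might infer several stronger things that the documents do not support:

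- **That a low baseline will always appear to predict response.** This depends on the response measure, on signed rather than absolute change, and on the SD ratio. Signed change is the natural reading, because the Aims 1-3 analysis treats benefit as directional, but the exploratory text does not say so.
- **That all the predictors are affected.** NIH Stroke Scale, Rankin score and laterality have no planned difference scores and are not directly coupled. For initial impairment the overlap is uncertain, since the term is undefined.
- **That 94% is the plan's own error rate.** The value 0.60 is given for gait speed only, and the median split and t-test are illustrative. The plan intends a series of regressions with predictor reduction and sets no cut-off.
- **That patients would be selected for treatment on this result.** The aim is labelled exploratory, and nothing commits to that use.

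**Conclusion.** The concern holds in conditional form. If response is defined wholly or partly on SIS-16 or the recruitment curve, the plan as written builds in a negative association between that measure's baseline and response, and its one safeguard cannot detect it. The direction is secure unless the follow-up SD is well above the baseline SD.

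The size is much less certain. Across the assumed r of 0.60 to 0.95 at n = 88, the false-positive rate runs from about 94% down to 21%. A composite response lowers it, and a response on gait speed alone removes the coupling for SIS-16. Even the mildest same-measure case examined (r = 0.95, active arm only, about 14%) exceeds the nominal 5%.

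The Aims 1-3 tests and the sample size are unaffected. The text should be corrected because, as it stands, a baseline finding from this aim could not be interpreted.

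**What to change.** Revise the Exploratory Aim in Data Analysis, and the matching text under Specific Aims, as follows:

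1. Name the outcome and time point that define response, and say what the initial impairment entry contains.
2. Do not relate a measure's own baseline to a response class built from its change.
3. Model the continuous follow-up value with its baseline as covariate, using both arms, and take the other predictors from the same model.
4. Judge whether a characteristic predicts benefit from tDCS by its predictor-by-arm term. Under the null the coupling is the same in both arms and cancels.
5. If a responder class is kept for the lesion-mapping step, state its measure and cut-off and label it descriptive.

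No new data are needed. The cost is wording and a little more analysis. The real downside is that interaction tests at 44 per arm have lower power, so the estimates should be reported with confidence intervals and as exploratory.

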In a pilot study investigating pairing locomotor training with transcranial direct current stimulation in patients with chronic stroke²³, our research collaborator at the University of Kentucky, [name], conducted a double-blind, randomized trial of active and sham tDCS (20 min at 2mA anodal stimulation over motor cortex) delivered just prior to locomotor training using a robotic gait orthosis treadmill. Eight participants (4 men, mean age=67.8; range=44-80) with chronic left hemisphere stroke (mean years post-stroke=4; range=1.1-11.6) were tested. Performance on a 10-meter walk test was the primary outcome measure, and assessments of functional ambulation category (FAC), timed up and go, balance, and the 16 item Stroke Impact Scale (SIS 16) were secondary measures. Improvement on the 10-meter walk test and the SIS 16 following active tDCS are shown in the figure - right. Active tDCS lead to greater improvement than sham tDCS on the FAC ($p=0.028$) and similar trends were evident for the SIS 16 ($p=0.062$) and the timed up and go test ($p=0.066$). This study shows that active tDCS augments gait training and function. The data were also used for power calculations.

Hypothesis and Specific Aims

Hypothesis: Increasing cortical excitability with active anodal tDCS prior to gait training will augment recover from a stroke.

Specific Aims:

1. Determine if active tDCS augments gait. Gait speed is a primary outcome measure. Spatiotemporal and kinematic gait assessment are secondary measures of gait. Over ground laboratory assessments of gait will measure 1) gait velocity and spatiotemporal gait measures using the GAITRite electronic walkway 2) ankle, knee, and hip angles using the SIMI motion analysis system. Changes in gait parameters will be expressed as difference scores from baseline. Difference scores will be compared between the active and sham groups to determine if tDCS augments gait parameters.

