Stroke subjects will be recruited via advertisement and from participants in past stroke studies who indicated a willingness to be contacted for additional studies. We will recruit participants > 3 months post unilateral, stroke to minimize confounding effects of spontaneous recovery. Subjects who participated in previous versions of the study will be re-contacted if they indicated they were willing to be contacted for additional studies.

Version 10 Revised 11/21/2014

Title: Using tDCS to Jump Start Gait Training and in Chronic Stroke Patients

PI: [name]

If they are willing to participate in the revised study they will be re-consented and re-enrolled under the new protocol.

Screening Procedures

All screening procedure will be conducted at either UAMS or UCA

For women of childbearing years a free pregnancy testing (urine dip stick test) will be required.

Administration of NIH Stroke Scale: administered and scored by study personnel who interview the participant. Severe language communication difficulties would preclude participation.

Administration of modified Rankin Scale: administered and scored by study personnel who interview the participant.

Administration of TMS Adult Safety Screening (TASS, determine study eligibility): by study personnel.

Medical records will be reviewed to evaluate participant's study acceptability and to obtain clinical studies including neuroradiological imaging studies.

MRI procedures

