- Stroke survivors > 3 months from most recent unilateral, stroke based on clinically or experimentally obtained MRI brain scans and behavioral evidence of stroke (e.g., risk factors, hemiplegia, unilateral sensory impairment, or localized higher cortical dysfunction) by report or in the medical record.
- Age: ≥21 years of age.
- Complete NIH Stroke Scale.
- Assessments performed at screening include the following:
 - Sufficient endurance, motor ability and balance to ambulate at least 10

Version 10 Revised 11/21/2014

meters continuously with moderate or less assistance.

- Demonstrate a gait impairment during ambulation such as gait instability or inefficient gait pattern
- Pass the Transcranial Magnetic Stimulation Adult Safety Screen (TASS) except for items related specifically to stroke and the treatment for stroke, i.e., neurologic injury, having a seizure related to stroke, or having a craniotomy for treatment related to stroke such as to relieve intracranial pressure.

Exclusion Criteria

- History of potentially fatal cardiac arrhythmias, such as ventricular tachycardia, supraventricular tachycardia, and rapid ventricular response atrial fibrillation with hemodynamic instability.
- Demand pacemakers or any other implanted electronic systems.
- Pregnant women, uncontrolled seizure disorder, Parkinson's Disease, Spinal cord injury, Traumatic brain injury with evidence of motor weakness, Multiple sclerosis.
- Documented episode in the medical record of a seizure occurring 1 month or more post stroke for which the patient received consultation or treatment for said seizure. Seizures occurring within the first month following a stroke are not exclusionary unless followed by another seizure.
- Fixed ankle plantar flexor contracture, peroneal nerve injury at the fibular head as the cause of foot-drop.
- History of dementia, severely impaired cognition, communication or comprehension deficits.
- Presence of severe or frequent headaches
- History of Botulinum toxin (Botox) injection to either of the lower extremities within the 3 month period preceding study entry.
- Have other medical conditions or are taking medications that compromise ambulation or balance.
- Failure to meet established screening criteria for TMS or tDCS (i.e., TASS - except as noted under inclusion criteria)
- Principal Investigator's or Medical Monitor's discretion not to include a participant

Additional Exclusion Criteria for MRI Scan

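### The exploratory response model omits time since stroke, so listed severity and function scores may be given weight that belongs to recovery stage

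*Combined protocol and SAP*

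**What the plan says.** **Predictor list (Data Analysis, Exploratory Aim).** The list begins "Predictors for 88 subjects include 1) NIH Stroke Scale score, 2) initial levels of impairment", continues "3) initial MT of the contralateral TA muscle (and recruitment curve parameters from the ipsilateral TA muscle" and ends "4) initial SIS-16 total and subscale scores, 5) stroke laterality, and 6) modified Rankin Scale scores". A series of regressions then cuts the list down, weighs the variables that remain and cross-validates them. Lesion mapping is added, which covers lesion site.

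**The aim itself (Hypothesis and Specific Aims, Exploratory Aim).** "Regression analyses will examine whether and how initial impairment, functional level, and cortical excitability predict a treatment response". Time since stroke is not one of these three domains.

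**Response definition.** Patients are classed by the magnitude of their difference scores. No adjustment for recovery stage is described.

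**Entry (Recruitment; Inclusion Criteria).** "We will recruit participants > 3 months post unilateral, stroke to minimize confounding effects of spontaneous recovery". The matching inclusion criterion reads "Stroke survivors > 3 months from most recent unilateral, stroke". Neither section states an upper limit.

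**Elsewhere.** Allocation is described only as block randomization, and the Aims 1-3 model contains group and assessment time. No section stratifies or adjusts for time since stroke.

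**The concern.** The plan treats spontaneous recovery as a confounder and handles it with an entry floor. A floor reduces the problem but does not remove it, because a patient just past 3 months and a patient many years out can both enter. Whatever dependence of change on recovery stage remains goes straight into the responder label, since that label is the size of the raw change.

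Stroke severity, Rankin score, SIS-16 and motor threshold may each vary with time since stroke. If one does, and time since stroke is not in the model, that variable can stand in for it. Cross-validation within the same sample would not expose this, because a proxy association repeats from fold to fold. At stake is the reading of the responder profile: a reader could take severity or function as mattering in its own right when its weight partly reflects how long ago the stroke happened.

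**Working it through.** The plan states no figure on this point, so there is none to reproduce. The check has two parts.

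**1. Is the variable really absent?** The six listed groups are NIH Stroke Scale, initial impairment, motor threshold with recruitment-curve parameters, SIS-16 total and subscales, laterality, and modified Rankin. None measures time since stroke. The aim statement, the lesion mapping, the randomization text and the Aims 1-3 model do not supply it either.

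**2. How large could the effect be?**

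Inputs:
- n = 88 (from the predictor list) and two-sided alpha 0.05.
- a = correlation of time since stroke with a listed predictor; b = its correlation with change. Neither is in the documents, so both are **assumptions**, shown over a range.
- The listed predictor has no effect on change once time since stroke is held fixed.

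With time since stroke left out, the predictor and change have correlation a × b. By Fisher's z,

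δ = atanh(ab) × √(n − 3), with √85 = 9.22

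rejection rate = Φ(δ − 1.96) + Φ(−δ − 1.96)

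Main range, a = b, with time since stroke explaining 5 to 10% of the variance in change:
- R² = 0.05, so a = b = √0.05 = 0.22 and ab = 0.05. δ = 0.0500 × 9.22 = 0.461. Rate = 0.067 + 0.008 = **7.5%**.
- R² = 0.10, so a = b = √0.10 = 0.32 and ab = 0.10. δ = 0.1003 × 9.22 = 0.925. Rate = 0.150 + 0.002 = **15.2%**.

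Simulation over a wider range (linear model on the change score, 4,000 datasets of 88 per setting):

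| a = b | ab | Time since stroke omitted | Time since stroke included |
|---|---|---|---|
| 0.2 | 0.04 | 6.6% | 5.2% |
| 0.3 | 0.09 | 13.4% | 4.9% |
| 0.4 | 0.16 | 32.1% | 5.3% |
| 0.5 | 0.25 | 65.7% | 4.8% |

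With a = 0 and b from 0.2 to 0.5, the rate with time since stroke omitted is 4.4 to 5.1%, so there is no inflation.

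**Dichotomized response.** The plan classifies patients rather than modelling a continuous score. The cut-point is not stated. With an assumed median split (20,000 datasets, linear test on the binary label), the rates are 6.5% at R² = 0.05 and 11.7% at R² = 0.10, against 7.4% and 15.4% for the continuous score in the same datasets. The pattern is the same and somewhat weaker.

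**The case against.** **Prediction is not causation.** The aim is to predict, and a score that carries information about recovery stage does predict change. Counting that association as a false positive is fair only if the weight is read as the score's own effect. This stands, and it limits the point to interpretation of the weights. The plan does intend to assess each variable's weight, so that reading is likely enough to guard against.

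**The large rates need strong assumptions.** A reader might infer from the lower rows of the table that false positives of 32 to 66% are to be expected. The documents do not support that. Those rows need correlations of 0.4 to 0.5, so time since stroke would have to explain 16 to 25% of the variance in change, and no document gives such values.

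**The pilot shows spread, not dependence.** The collaborator's pilot reports "mean years post-stroke=4; range=1.1-11.6". That comes from eight patients, all well past 3 months. It shows that time since stroke can vary widely, not that change depends on it. How many patients will enter soon after 3 months is not stated.

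**Known for everyone?** A reader might infer that the exact interval is already held for every participant. Eligibility requires showing more than 3 months, by report or record, which does not need an exact date. No data field for the interval is described.

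**Aims 1-3.** A reader might infer that the main treatment comparison is biased. It is not, because allocation is random. Only precision is at stake there.

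**An open list.** The list is introduced by a word that need not be exhaustive, and the aim is exploratory. That is true, but a variable that is not named is not pre-specified, and nothing in the documents adds this one.

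**Conclusion.** The omission is real and worth a small correction. The plan itself links time since stroke to confounding, admits patients with no upper limit, defines response by unadjusted change, and then leaves the variable out of its predictor list.

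The size cannot be established from the documents. Under assumed equal correlations of 0.22 to 0.32, the chance of declaring a predictor with no independent effect significant is about 7 to 15% rather than 5%. It is higher only under stronger assumed correlations, and not inflated at all if the predictor is unrelated to time since stroke. The point concerns the exploratory aim and how its weights are read. It does not touch the validity of the randomized comparison.

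**What to change.** 1. Record at screening the interval from the most recent stroke to baseline, and whether it comes from the medical record or from patient report.
2. Add that interval (for example, log months) to the exploratory list as a pre-specified predictor, and report the weights of the other predictors adjusted for it. For that to hold, it should stay in the models while the list is being reduced.
3. Optionally, include it as a baseline covariate in the Aims 1-3 group comparison, for precision only. The residual between-patient variance of the difference scores would fall by the share it explains: 5 to 10% if R² is 0.05 to 0.10, which is again an assumption.

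**Cost.** One recorded field, which for some patients may rest on report and so be imprecise, one line in the predictor list, and one degree of freedom.

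**What it does not do.** Adding this variable does not separate response to tDCS from response to gait training. The plan describes no predictor-by-arm term, and a seventh predictor does not supply one.
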